7.7 Reporting of SAEs

The PI and site PI should be notified of all SAEs within 24 hours of the investigator becoming aware of the event. The AE CRF must be completed. Investigators should notify the PI and site PI of all SAEs occurring from the time of randomization until 28 days after the last protocol treatment administration (through Week 8). SARs and SUSARs must be reported until trial closure.

The study site is responsible for the reporting of SAEs, SUSARs, and other SARs to the regulatory authorities and the research ethics committees, as appropriate. The PI and/or site PI will review all SAE reports. SAEs and SUSARs must be then reported to the competent authorities within 7 days.

Reporting will be submitted to the local IRB as per their specified reporting requirements. Copies of each report and documentation of IRB notification and receipt will be kept in the regulatory binder. At the time of the initial report, the study identifier, participant identification number, date of event, description of event, relationship to linezolid or rifampicin, intervention if any, working diagnosis, and current vital status will be provided.

Within the 7 days of the initial report (or concurrently), the investigator will provide further information on the AE Reporting CRF in the form of a written narrative. This will be documented along with any other diagnostic information that will assist understanding of the event. Significant new information on on-going SAEs will be provided promptly to the study sponsor and local IRB. Serious AEs that are still on-going at the end of the reporting period must be followed up to determine the final outcome. Grade 3-4 AEs that are not serious and unrelated to the investigational medicinal product will be reported in aggregate in a safety report.

7.8 Independent Data Safety Committee

The study will undergo interim review by the appointed Data Safety and Monitoring Board, which will include expertise in statistics, clinical trials, and HIV/TB co-infection, after 30 participants have completed the Week 8 visit, or no more than nine months after the enrollment of the first study participant. An interim review may also be convened if a concern is identified by the PI, site PI, other study team member in consultation with the team, IRB, or regulatory authorities. The DSMB will be separate from the investigators and will have full access to all accumulating data on safety and efficacy. The DSMB can also modify the frequency of interim analysis.

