- **DESIGN** ALTER is a phase II randomized, open-label trial using a factorial design of high or standard dose rifampicin with or without linezolid for the first 4 weeks of treatment for tuberculous meningitis (TBM). Initial randomization will be to high (35 mg/kg/day) versus standard (10 mg/kg/day) dose oral rifampicin for 4 weeks. After randomization to high versus standard dose rifampicin, participants will undergo a second randomization to linezolid 1200 mg daily versus no linezolid for 4 weeks.
- DURATION 24 weeks
- SAMPLE SIZE 60 participants
- **POPULATION** Participants with definite, probable, or possible TBM, aged \geq 18 years
- SETTING Masaka Regional Referral Hospital, Masaka, Uganda
- **STRATIFICATION** Participants will be randomized with stratification by HIV status and stage of disease (Grade 1 vs. 2 and 3), as defined by the modified British Medical Research Council criteria.
- **REGIMEN** Participants will first be randomized 1:1 to:

High dose rifampicin 35 mg/kg for 4 weeks vs. standard dose rifampicin 10 mg/kg

Participants will then be randomized 1:1 to:

Linezolid 1200 mg daily for 4 weeks vs. no linezolid (see **Table 1**)

In addition, all participants will receive standard treatment for TBM with isoniazid 5 mg/kg/day, pyrazinamide 25 mg/kg/day, ethambutol 20 mg/kg/day, corticosteroids (IV dexamethasone 0.4 mg/kg/day for 1 week, 0.3 mg/kg/day for 1 week, followed by a prednisone taper over 6 weeks), and vitamin B₆ 50 mg daily. After the first 4 weeks of therapy, participants in the high dose rifampicin arm (Arm A) will receive standard dose oral rifampicin (10 mg/kg/day) for another 11 months as per national guidelines.

		RI	F
colid		High dose (35 mg/kg)	Standard dose (10 mg/kg)
inez	+	Arm A: R ₃₅ HZEL	Arm B: R ₁₀ HZEL
	-	Arm C: R ₃₅ HZE	Arm D: R ₁₀ HZE

 Table 1: Study regimens

R, rifampicin; H, isoniazid; Z, pyrazinamide; E, ethambutol; L, linezolid

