1.0 BACKGROUND AND STUDY RATIONALE

Although TBM is the most devastating form of TB, it has largely been neglected in the global health research agenda. Even with appropriate therapy up to 50% of patients with TBM die, most within the first month after presentation.¹⁻³ Of those who survive, neurologic disability is common.⁴⁻⁶ Despite these bleak outcomes, a paucity of data exists on the optimal approach to TBM treatment, including for people living with HIV (PLWH).

A targeted approach to TBM management must leverage drugs that penetrate the CNS. In the absence of large-scale trials, the same standard drug regimens and dosing used for pulmonary TB—rifampicin (RIF), isoniazid (INH), pyrazinamide (PZA), and ethambutol (EMB) for two months (intensive therapy), followed by RIF and INH in the continuation phase—are empirically employed for TBM, except with a longer continuation phase to complete 9 to 12 months of therapy. This generic approach assumes that the efficacy of TB drugs is equivalent at all sites of infection, disregarding the unique challenges of infection of the CNS.⁷ Effective drugs for TBM must penetrate the blood brain barrier (BBB) and remain in the CNS to achieve bactericidal drug concentrations.⁸

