7.4 Expected disease-related events

This study population, with TB and advanced HIV, are both critically ill and profoundly immunosuppressed will have a complicated clinical course. Opportunistic and nosocomial infections are expected. Disease-related events will be frequent and include:

- Death due to TBM (~40% enrolled participants). Will always be reported as an SAE.
- Disability due to TBM. Will not be reported as an AE.
- TBM-IRIS events and symptoms. Will not be reported as an AE.
- Neurological complications of TBM, including tuberculoma, infarct, seizures, headache due to raised ICP. **Will not be reported as an AE.**
- Other opportunistic infections. Will not be reported as an AE.
- Nosocomial infections, including hospital acquired pneumonias or aspiration pneumonias. Will not be reported as an AE.

Expected disease-related events do not require reporting unless the severity of the event was considered to be unexpected.

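### The 30-participant limb of the DSMB trigger leaves out anyone who dies or leaves before Week 8, so if accrual exceeds about 4 per month, early mortality can delay the planned review, up to the nine-month limit

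*Combined protocol and SAP*

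**What the plan says.** Section 7.8 (Independent Data Safety Committee) sets the planned interim review in one sentence with two limbs. The count limb is "after 30 participants have completed the Week 8 visit". The calendar limb follows at once: "or no more than nine months after the enrollment of the first study participant". I read the pair as whichever comes first, although the text does not say so in words.

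The same section provides other routes. "An interim review may also be convened if a concern is identified by the PI", and the site PI, other team members, the IRB and regulators are also named. The board has "full access to all accumulating data on safety and efficacy", and "The DSMB can also modify the frequency of interim analysis".

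On mortality, section 7.4 lists among the expected events "Death due to TBM (~40% enrolled participants", with no time point. Section 1.0 says that up to half of patients die even with appropriate therapy, "most within the first month after presentation". The synopsis sets the sample size at 60. No accrual rate is stated anywhere.

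**The concern.** A participant who dies in week 2 never completes a Week 8 visit and so adds nothing to the count of 30. In a disease where deaths are frequent and early, the count limb therefore slows as mortality rises. That runs against the purpose of a safety review, which is chiefly to protect participants not yet enrolled. The more deaths there are before Week 8, the more people must be randomised before this limb calls for a look. With only 60 participants in all, a delay of one to three months can use up most or all of the remaining enrolment.

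**Working it through.** The trigger is a design choice with no calculation behind it, so there is no stated figure to reproduce. The check asks when the review falls, and how many are enrolled by then, with and without early deaths in the count.

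**Inputs from the protocol:** 30 completers and nine months (7.8); 60 participants (synopsis); about 40% mortality with no time point (7.4).

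**Assumptions:**
- Accrual *a* is 4 to 8 per month and steady.
- The share dead before Week 8, *m*, is 25% to 40%. The upper value supposes that every expected death falls before Week 8.
- Other dropout is ignored, and enrolment is capped at 60. Section 3.3 replaces late exclusions, so the true total could be a little higher.
- Eight weeks = 56/30.4375 = 1.84 months.

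**Enrolment that must mature for 30 completers:** 30/(1 − m). At 25% this is 30/0.75 = 40. At 40% it is 30/0.60 = 50. If early deaths count, it is 30 whatever the mortality.

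**Review month:**
- As written: min[30/((1 − m)a) + 1.84, 9].
- Early deaths counted: min[30/a + 1.84, 9]. This is slightly late, because it credits a death only at its 8-week date.

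**Enrolled at review:** min[a × review month, 60].

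| Accrual per month | Review month, deaths counted | Review month, as written, 25% / 40% | Enrolled, deaths counted | Enrolled, as written, 25% / 40% |
|---|---|---|---|---|
| 4 | 9.0 (limit) | 9.0 / 9.0 (limit) | 36 | 36 / 36 |
| 5 | 7.8 | 9.0 / 9.0 (limit) | 39 | 45 / 45 |
| 6 | 6.8 | 8.5 / 9.0 (limit) | 41 | 51 / 54 |
| 7 | 6.1 | 7.6 / 9.0 | 43 | 53 / 60 |
| 8 | 5.6 | 6.8 / 8.1 | 45 | 55 / 60 |

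Example at 6 per month and 25%: 40/6 + 1.84 = 8.51 months, and 6 × 8.51 = 51 enrolled. With deaths counted: 30/6 + 1.84 = 6.84 months, and 6 × 6.84 = 41.

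**Delay due to the wording:** 1.2 months at 5 per month (9.0 − 7.8); 1.7 to 2.2 at 6; 1.4 to 2.9 at 7 (10/7 and 20/7); 1.3 to 2.5 at 8 (10/8 and 20/8).

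**Accrual at which the count limb fires before month 9:** [30/(1 − m)]/(9 − 1.84).
- Deaths counted: 30/7.16 = 4.2 per month.
- As written, 25%: 40/7.16 = 5.6 per month.
- As written, 40%: 50/7.16 = 7.0 per month. By that review, 50 + 1.84 × 7 = 63 would have been enrolled, which exceeds 60. At 40% early mortality the count limb therefore cannot bring the review before both month 9 and the end of enrolment.

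**The case against.** The strongest reply is that the nine-month limit already protects against this, and much of that reply stands. A reader who stops at the count limb might infer that every death postpones the review, that the delay has no bound, or that the review might never take place. The documents support none of these. Deaths after Week 8 have no effect. No death moves the review once the calendar limb governs, which on these figures means accrual of about 4 per month or less. The review cannot fall after month 9 in any case.

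The size also rests on two figures that the documents do not give. This is a single hospital with a long list of exclusions, and nothing shows that accrual will exceed 4 per month. The 40% has no time point. Even with early deaths counted, 39 to 45 of 60 are enrolled at the review at 5 to 8 per month, so the amended wording gives an earlier review, not an early one.

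Nor would it be right to infer that early deaths go unseen. Section 7.4 says that deaths are always reported as SAEs, and section 7.7 sends SAEs to the PI and site PI within 24 hours. Those people can call a review, and the board can change its schedule. But these routes depend on someone judging that there is a concern. Section 7.7 sends SAE reports to the PI, site PI, authorities, ethics committees and sponsor, and does not name the DSMB. Deaths from the disease are expected here, so a moderate excess may not look like a concern until the arms are compared. The discretionary routes reduce the risk; they do not repair the scheduled trigger.

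**Conclusion.** The point holds in a bounded form. The count limb excludes participants who die or leave before Week 8. Where accrual is above about 4.2 per month, higher early mortality makes the planned review later, up to month 9. With 25–40% dead by Week 8 and accrual of 5 to 8 per month, the delay is about 1.2 to 2.9 months. Between 0 and 15 participants then remain to be enrolled at the review, against 15 to 21 if early deaths counted. At 4 per month or less there is no difference.

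Confidence is high that the wording leaves early deaths out of the count, and lower for the consequence, because accrual and Week 8 mortality are both assumed. This is a worthwhile, inexpensive improvement to a rule that already has a backstop, and not a serious defect.

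**What to change.** Replace the trigger in section 7.8, and in the DSMB charter if there is one, with wording such as:

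*after 30 randomised participants have reached 8 weeks after randomisation, or died or left the study earlier, or nine months after first enrolment, whichever is first.*

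This makes the count limb independent of mortality and states outright that the earlier date applies. Apart from the seven-day window on the Week 8 visit, it cannot make the review later at any accrual rate.

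The cost is one sentence, and fewer complete Week 8 records in the review. That loss is modest: the early deaths are themselves key safety data, and the randomised treatments last only 4 weeks.

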8.0 CLINICAL MANAGEMENT ISSUES

Criteria for participant management, dose interruptions, modifications, and discontinuation of treatment are mandated only for toxicities attributable to study-provided drugs. The PI and site PI must be notified within 24 hours regarding toxicities that result in a change in study treatment (including transient or permanent discontinuation) during the study-defined treatment period (first 4 weeks).

8.1 Toxicity Management

Only toxicities Grade 3 or higher related to study medications provided through the study (linezolid, rifampicin) will be considered in the toxicity management section. For toxicities potentially attributed to one or more of the study medications, one or more of the study medications may be held or permanently discontinued.

8.1.1 Liver toxicity

A liver toxicity management plan will be implemented if either of the criteria outlined below are met:

- ALT > 5x the upper limit of normal (ULN)
- ALT > 3x ULN with signs or symptoms suggestive of clinical hepatitis including one or more of the following: nausea, vomiting, abdominal pain, dark or clay colored stools, unexplained fever, jaundice, liver tenderness, or hepatomegaly

Management plan:

- 1. Discontinue pyrazinamide
- 2. Assess for use of other hepatotoxic drugs and discontinue potentially hepatotoxic, nonessential medications (e.g., co-trimoxazole, fluconazole)
- 3. Repeat ALT, bilirubin, and INR every 2 (+/-1) days
- 4. If the transaminases fall to <5x ULN and symptoms resolve, continue treatment without pyrazinamide.
- 5. If the transaminases do not fall to <5x ULN or bilirubin is >2.0 mg/dL or INR >1.5, or symptoms worsen, stop rifampicin and isoniazid, and start alternative regimen for TB meningitis (e.g., streptomycin and fluoroquinolone).
- 6. Continue to follow ALT every 2 (+/-1) days until stable. If the ALT return to <2x ULN and symptoms resolve, rifampicin will be restarted. If ALT remain stable after a minimum of 7 days, isoniazid will be restarted, and streptomycin and fluoroquinolone stopped.
- 7. Continue to follow ALT every 2 (+/-1) days until stable. If ALT begin to rise again to >5x ULN after reintroduction of either rifampicin or isoniazid, stop the offending medication. Depending on which medication has to be stopped (or potentially both), treat with 1) streptomycin, fluoroquinolone, and ethambutol OR 2) rifampicin, fluoroquinolone, and ethambutol OR 3) isoniazid, fluoroquinolone, and ethambutol.

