8.1.6 Other toxicities

Grade 2 toxicities: For grade 2 toxicities, the participant will be followed more carefully, with additional laboratory and/or clinic visits as necessary, and the study drugs temporarily held at the investigator's discretion.

Grade 3 toxicities: For any grade 3 toxicity that, in the investigator's judgment is due to rifampicin or linezolid, the causative drug should be held. The clinician should rule out other possible causes of the symptoms before discontinuing study medication. When possible, concomitant medications should be held first at the discretion of the investigator if he/she suspects they are contributing to the toxicity. Depending on the nature and severity of the toxicity, the degree to which it resolves, and/or the emergence of alternative explanations for the toxicity or the subject's deterioration, the study drugs(s) may be restarted at the discretion of the investigator.

Grade 4 toxicities: Any participant with grade 4 renal, hepatic, cardiac, hematological, or neurologic toxicity will be immediately discontinued from study therapy. The laboratory test or clinical finding in question will be reassessed as soon as possible. The repeat test will guide management of the event as follows:

- 1. If the repeat assessment shows toxicity of grade 3 or lower, and if the participant has continued to receive study drugs between the two testing dates, then the participant will be managed according to the appropriate toxicity level of the repeat test.
- 2. If the repeat test shows toxicity of grade 3 or lower, and if the participant has not received study drugs between the two testing dates, then the participant will be managed at the discretion of the investigator with regard to the re-administration of study drugs, and otherwise according to the toxicity level of the repeat test.
- 3. If the repeat test shows grade 4 toxicity, then the participant will be permanently discontinued from study medications unless a clear alternative cause for the toxicity has been identified, in which case, re-administration of study drugs may be considered but only with prior approval from the PI and site PI. Further treatment of TB will be directed by the investigator and treating clinician on an individualized basis. The participant will continue to be followed for study monitoring purposes (as are other participants who make a permanent departure).

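### For grade 4 liver toxicity, sections 8.1.1 and 8.1.6 give incompatible rifampicin rules, and nothing says which prevails

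*Combined protocol and SAP*

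**What the plan says.** Section 8.0 makes the management rules mandatory for toxicity attributable to study-provided drugs. Section 8.1 identifies these as linezolid and rifampicin. Under section 5.2 the study supplies the single-drug rifampicin 300 mg tablets and the linezolid; the fixed-dose combination tablets are routine care.

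Section 8.1.1 (Liver toxicity) starts at ALT above 5 times ULN, or above 3 times ULN with symptoms of hepatitis. Step 1 stops pyrazinamide. Step 3 repeats ALT, bilirubin and INR every 2 (+/-1) days. Step 5 applies if transaminases do not fall below 5 times ULN, "or bilirubin is >2.0 mg/dL or INR >1.5, or symptoms worsen, stop rifampicin and isoniazid". Step 6 then says: "If the ALT return to <2x ULN and symptoms resolve, rifampicin will be restarted". Isoniazid follows later: "If ALT remain stable after a minimum of 7 days, isoniazid will be restarted". Linezolid is not mentioned.

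Section 8.1.6 (Other toxicities) says: "Any participant with grade 4 renal, hepatic, cardiac, hematological, or neurologic toxicity will be immediately discontinued from study therapy". A repeat test then decides. Item 3 reads: "If the repeat test shows grade 4 toxicity, then the participant will be permanently discontinued from study medications". The exception is a clear alternative cause, in which case re-administration "may be considered but only with prior approval from the PI and site PI". After permanent discontinuation, "Further treatment of TB will be directed by the investigator and treating clinician on an individualized basis".

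**The concern.** Both sections reach the same participant: one whose liver event is grade 4, meets the ALT trigger and is attributed to a study-provided drug. One section directs that rifampicin come back once ALT has settled; the other rules out study-supplied rifampicin unless two conditions are met. They also differ on the day of detection, when the decision is most urgent.

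What is at stake is patient safety and consistent conduct. In arms A and C the study-supplied rifampicin is the supplement that takes the dose from about 10 to about 35 mg/kg. Whether a participant with grade 4 liver injury takes further doses of it, or returns to it later, would depend on which section the site staff followed.

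**Working it through.** No figure in the plan is being tested, so the check sets the two rules side by side and then asks how many participants they could touch.

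**1. Do the rules overlap?** The 8.1.1 trigger has no upper ALT limit and no grade 4 exception. The grading table's ALT cut-off for grade 4 is not printed in the documents. If it is at or above 5 times ULN, every grade 4 ALT falls inside 8.1.1; if it were lower, the rules would still overlap above 5 times ULN. Section 8.1.6 names hepatic toxicity. The rules therefore overlap.

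**2. Do they agree?** This takes grade 4 ALT to be at or above 5 times ULN.

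| Stage | 8.1.1 | 8.1.6 | Result |
|---|---|---|---|
| Detection, bilirubin and INR within limits (say 1.5 mg/dL and 1.2), no symptoms | Pyrazinamide stopped; rifampicin continues by implication until a step 5 criterion is met | Study therapy stopped at once | Compatible only if 8.1.6 adds to 8.1.1 |
| Detection, bilirubin 2.5 mg/dL | Step 5 stops rifampicin | Study therapy stopped | Agree on rifampicin |
| Repeat test grade 3 or lower, off drug | Step 6 threshold for restart | Investigator's discretion | Compatible; discretion can follow step 6 |
| Repeat test still grade 4 | Rifampicin stopped under step 5 | Study medications permanently stopped | Agree for now |
| Later, ALT below 2 times ULN and symptoms resolved | Rifampicin is to be restarted | Study-supplied rifampicin stays off without a clear alternative cause and prior approval | **Contradiction** |

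Section 8.1.6 is also not quite consistent about the immediate stop, since item 1 provides for the case "if the participant has continued to receive study drugs between the two testing dates".

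**3. Does any text rank them?** Sections 8.0 and 8.1 set scope; the statement in 8.1 that study medications may be held or stopped is permissive. Section 8.1.7 points back to the toxicity section as a whole. Section 9.1 lists toxicity requiring permanent discontinuation without saying when it is required. None sets precedence.

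**4. Size.** Assume equal arms: 60 / 4 = 15 per arm.
- Rifampicin supplement (arms A and C): 15 + 15 = 30 participants.
- Any study-supplied drug (arms A, B and C): 45.
- Supplement dose from Table 4: 3, 4, 5 or 6 tablets of 300 mg = 900, 1200, 1500 or 1800 mg/day, on top of 300 to 750 mg in the combination tablets.
- Doses at issue before the first repeat test (day 1 to 3 under step 3): 0 to about 3.

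The documents give no grade 4 hepatic rate. Purely as assumptions, rates of 0.5% and 1% give 30 x 0.005 = 0.15 and 30 x 0.01 = 0.30 expected cases. The chance of at least one, 1 - (1 - p)^30, is then 14% and 26%.

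**5. Time window.** Study dosing lasts 4 weeks, and liver tests after entry are scheduled at weeks 1, 2 and 4 (Table 5). A restart of study-supplied drug is therefore a live question mainly for events found by week 2 that resolve before week 4.

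**The case against.** The best defence is the heading of 8.1.6: if it covers only other toxicities, liver events belong to 8.1.1 alone. This fails. The grade 4 paragraph names hepatic, hematological and neurologic toxicity, each of which has its own subsection, and a separate sentence then deals with other grade 4 toxicities.

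A second defence is that the rules are cumulative at detection. 8.1.1 never orders rifampicin to be continued at that moment, so a site could stop pyrazinamide and study therapy on the same day. This stands in part. A reader might infer that staff cannot obey both sections at detection, and the text does not support that. Both can be obeyed, but only on a reading that the protocol does not state.

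Third, step 6 gives no dose or product, fixed-dose rifampicin is routine care, and treatment after permanent discontinuation is individualised. Step 6 could thus mean standard-dose rifampicin only, with the supplement left off. That reading is sensible and the fix adopts it, but the present wording does not limit the restart in that way.

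Fourth, section 8.0 requires the PI and site PI to be told within 24 hours of toxicities that change study treatment. This helps, but notification is not the prior approval that item 3 asks for, and it does not settle which rule applies.

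Two stronger readings are tempting:
- **A linezolid conflict.** Each participant affected would move linezolid completion by 1/30 = 3.3 percentage points. But 8.1.1 is silent on linezolid and 8.1.6 stops it, so an effect arises only if staff let silence override an express instruction.
- **A likely occurrence.** Section 1.0 quotes transaminitis in 0 to 2.5% on rifampicin monotherapy. Used as a grade 4 rate, 2.5% gives 1 - 0.975^45 = 68% for at least one case among 45. That figure is not stated to be grade 4, and the same section considers isoniazid and pyrazinamide the likelier causes. The 68% is not a supported estimate.

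**Conclusion.** The point holds for rifampicin. After a confirmed grade 4 hepatic result, 8.1.1 step 6 and 8.1.6 item 3 contradict each other on study-supplied rifampicin. At detection they are reconcilable only through an additive reading that is nowhere written. Linezolid is not a direct conflict.

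The scope is narrow: study-supplied drugs, within the 4-week intervention period, in about 30 participants for rifampicin if the arms are equal. Few cases are expected, although the number cannot be estimated from the documents. Sample size, power and alpha are unaffected. The change should be made because a rule for a serious toxicity ought to give one instruction. The conclusion assumes that study medications in item 3 means the study-supplied drugs, as 8.1 suggests, and that grade 4 ALT lies at or above 5 times ULN.

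**What to change.** Add the following to both 8.1.1 and 8.1.6:

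> For grade 4 hepatic toxicity, 8.1.6 governs the study-supplied drugs: the high-dose rifampicin supplement and linezolid are held the same day and, if the repeat test is still grade 4, are not restarted except under 8.1.6 item 3. 8.1.1 continues to govern pyrazinamide, isoniazid, standard-dose rifampicin, the alternative regimen and monitoring; a step 6 restart after confirmed grade 4 toxicity is at standard dose (10 mg/kg) only.

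A practical note: step 6 brings rifampicin back at least 7 days before isoniazid, so combination tablets cannot be used in that interval. The pharmacy should know which single-drug product to dispense at standard dose.

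The cost is amendment wording in two subsections, with no new tests, visits or participants. The downside is that some participants lose their remaining high-dose rifampicin or linezolid doses, as 8.1.6 already requires.
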